Intradialytic exercise has been a subject of several investigative studies for the past several decades. A Cochrane systematic review in 2011 found there to be significant benefit in patient's aerobic capacity, resting blood pressure, and health-related quality of life from exercising three times per week for greater than 30 minutes per HD session.⁵ There have been several examples in the literature of exercise studies and subsequent meta-analysis that have shown improvement in many of the physical fitness tests used to measure frailty such as the 6 minute walk test (6MWT), Timed Get up and Go Test (TUG), Maximum Walking Speed Test, Sit to Stand Test (STS) and overall metabolic equivalents achieved.^{6,7,8,9} These exercise routines usually involve either aerobic exercise, resistance exercise or a combination of the two for at least 30 minutes during the 1st two hours of

each HD session. The use of resistance exercises via elastic bands alone has been shown to improve the patient's 30 second STS test and 8-foot TUG test.¹⁰

Despite the known benefits of exercise, there are no formal intradialytic exercise protocols in the United States. The main barriers in the US are thought to be interference with the workflow of an outpatient dialysis center as well as high rates of patient non-adherence and drop out. A German single-center long term study employing exercise professionals measured 1 and 5-year adherence at 78% and 43% respectively.¹¹ Unfortunately the data on adherence and efficacy in the United States is lacking. This remains a challenge across the world as nephrologists and dialysis center staff are thought to lack the personnel and resources needed to advise dialysis patients on individualized exercise regimens.¹²

A test of the feasibility and efficacy of an intradialytic exercise (IDEx) strategy will be the primary intent of this project. This IDEx study will consist of an exercise physiologist consultation with HD patients once a week during their 3 times weekly in-center HD sessions over a 3-month period. At these consultations, exercise physiologists will perform physical assessments and develop individualized resistance exercise plans using elastic bands. The exercise physiologist will continue to visit with the patient once weekly after the initial consultation over the 3-month period. The effects of the resistance exercise regimens on physical function will be measured.

2. Study Aims

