The primary objective of this study will be to test the feasibility and efficacy of a 3 month exercise physiologist consultation program. Specifically, our aims will be to:

- a. Test the feasibility of a 3-month exercise physiologist led program
- b. Measure the effect of an exercise physiologist collaboration and intradialytic exercise on the physical function of HD patients using the 30 second STS test,

handgrip strength test [required for frailty scale], 8-foot TUG test and patient physical activity based off of the Low Physical Activity Questionnaire.

3. Administrative Organization

The study will be administered from Satellite Healthcare, Inc., [name]. The study site will be Satellite Healthcare Milpitas. [name].

4. Study Design

a. Experimental design of the study

Randomized controlled trial (RCT) proof of concept study design

b. Study population

Convenience sample from prevalent HD patients from Satellite Milpitas Hemodialysis center in Northern California.

c. Sample size

n=50 (25 intervention - 25 control)

d. Study Outcomes

Feasibility outcomes

- Adherence calculated as the total number of self-reported exercise sessions attempted by the patient when EP not present divided by the total number of hemodialysis sessions. This information will be collected from the patient at the weekly meeting with the EPs.
- Adverse events defined as any injury, impairment or medical condition that was directly or suspected to be due to performing the prescribed exercise.

Efficacy Outcomes

- Change in physical function as measured by the 30 second sit to stand test (STS), handgrip strength test (HGST) and the 8 foot timed up and go test (TUG). Performed prior to initiation of dialysis at their mid-week dialysis session.

5. Study Procedures

a. Subject selection procedures

The Principal Investigator is responsible for screening subjects for the study, ensuring subjects meet all inclusion criteria.

b. Inclusion criteria

- Age 18 years or greater
- Ability to understand and communicate English
- Diagnosis of ESRD and currently undergoing in-center hemodialysis
- On HD for longer than 6 weeks
- Approved by the Satellite Milpitas Medical Director and/or referring physician

c. Exclusion criteria

- Previous major amputations
- Inability to independently ambulate
- Known to be pregnant

d. Recruitment procedures

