- A modified version of the Fried Frailty Index Score will be used to assess for the presence of frailty in both groups at the start of the study. The modification will be the replacement of the Minnesota Leisure Time Activity Questionnaire (MLTAQ) used to measure the low physical activity portion of the FFI with the Low Physical Activity Questionnaire

(LoPAQ). This was previously compared to the MLTAQ in a study of dialysis patients¹⁴.

- Exercise physiologist will encourage patients to complete their individualized exercise routines during their dialysis sessions for which the EP is not present but also at home at their convenience.
- Adverse events can be reported directly to the center manager or the PI. The EP will ask directly about adverse events at every meeting.

6. Data Analysis Plan

Demographic data: age, gender, ethnicity, weight, BMI, end stage kidney disease cause, co-morbid conditions, vintage on dialysis, dialysis treatment details and biochemical indices will be collected. Paired t-test or Wilcoxon-sign-rank will be used to compare the pre and post intervention STS, Hand Grip Test, TUG and modified FFI results depending on the distribution of the data. Patients who drop out or withdraw from the study will be included in the final outcomes with intention-to-treat analysis.

7. Timeline

Timeline (months)	1	2	3	4	5	6	7
Refine protocol							
Staff in-services							
Patient recruitment							
Exercise physiology intervention							
Evaluation interviews							
Data cleaning							
Data analysis							
Papers/Report write up							

IDEx Data Collection Plan

Test	Initial Assessment	Week 1	Week 2	Week 3	Week 4	Week 5	Week 6	Week 7	Week 8	Week 9	Week 10	Week 11	Week 12
Demographic 
 • Name/MR No. • DOB/Age • Gender • Racial Origin • Height • Smoker • Dialysis Vintage (months) • Renal Disease 	x												
Comorbidities 
 • Lung • PVD • Cerebral • Diabetes • Hypertension • Heart Failure 	x												
Dialysis Info 
 • Weight (dry) • BMI • KtV • Hb, PO4, K • Blood Pressure 	x												
Physical Function Tests 
 • Sit to Stand • Timed up and go • Hand Grip 	x											x	
Modified Fried Frailty Index	x											x	
EP Meeting Record	x	x	x	x	x	x	x	x	x	x	x	x	x

References

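### Efficacy is part of the primary objective, but it rests on up to five unranked measures with no primary efficacy outcome, testing order or error control

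*Combined protocol and SAP*

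**What the plan says.** Section 2 states: "The primary objective of this study will be to test the feasibility and efficacy of a 3 month exercise physiologist consultation program". Feasibility and efficacy stand together there, and neither is ranked above the other.

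The efficacy measures are listed in three places, and the lists differ:

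- **Section 2, aim b:** the 30-second sit-to-stand test (STS), followed by "handgrip strength test [required for frailty scale], 8-foot TUG test and patient physical activity based off of the Low Physical Activity Questionnaire". Four measures.
- **Section 4d, Efficacy Outcomes:** "Change in physical function as measured by the 30 second sit to stand test (STS", with grip and TUG alongside. Three measures in one bullet.
- **Section 6:** "Paired t-test or Wilcoxon-sign-rank will be used to compare the pre and post intervention STS, Hand Grip Test, TUG and modified FFI results". Four measures, with the modified Fried Frailty Index (FFI) in place of the Low Physical Activity Questionnaire (LoPAQ).

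Together they name five: STS, grip, TUG, modified FFI and LoPAQ activity. No section calls any of them primary. The documents give no significance level, testing order, multiplicity adjustment, success criterion or sample-size calculation. Section 4 describes a randomised proof-of-concept trial with 25 patients per arm, but Section 6 describes no comparison between the arms.

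**The concern.** A trial that sets out to test efficacy needs to say which result would count as showing it. Here several measures are each tested and nothing says which one carries the conclusion. If one of three or four tests came out significant, nothing in the plan would stop that measure from being headlined after the results are seen, and nothing would show the reader that it had been selected. The error rate of the efficacy conclusion is therefore undefined.

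The scoring rules widen the choice. Attachment b averages three grip readings, whereas the Pre and Post Intervention Assessment form asks for the best of three (while also providing a box for the average). For TUG, Attachment c records the faster of two trials and the form asks for their average. At stake is a decision, after a 50-patient study, on whether the programme works well enough to take further.

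**Working it through.** **Inputs from the documents.** Three measures (Section 4d) or four (Section 2; Section 6), five distinct; 25 per arm (Section 4c); paired t-test or Wilcoxon signed-rank test (Section 6).

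**Assumptions, not in the documents.** Two-sided 0.05 per test; equal pairwise correlation r between test statistics, from 0 to 0.7, with 0.9 as a sensitivity check; no dropout. The plan states no error rate, so there is no figure of its own to reproduce.

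**Step 1. At least one significant result in either direction, no true effect.** For k independent tests the chance is 1 − 0.95^k:

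- k = 3: 1 − 0.8574 = 14.3%
- k = 4: 1 − 0.8145 = 18.5%
- k = 5: 1 − 0.7738 = 22.6%

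For correlated tests, simulation of equicorrelated normal statistics (1,000,000 draws) gives:

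| Measures tested | r = 0 | r = 0.5 | r = 0.7 | r = 0.9 |
|---|---|---|---|---|
| 3 | 14.3% | 12.5% | 10.9% | 8.4% |
| 4 | 18.5% | 15.6% | 13.0% | 9.4% |
| 5 | 22.6% | 18.3% | 14.9% | 10.2% |

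Simulated t-tests with n = 25, both paired and 25 against 25, agree: about 11–14% for three measures and 13–18% for four.

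**Step 2. Favourable direction only.** A chance worsening cannot be presented as efficacy. With independent tests the chance is 1 − 0.975^k: 7.3% for three and 9.6% for four. At r = 0.7 the simulation gives 5.5% and 6.5%. A single test gives 2.5%, so the inflation is between 5.5/2.5 = 2.2 and 9.6/2.5 = 3.8 times.

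**Step 3. What the paired test adds.** Steps 1 and 2 take each test to be a valid test of no treatment effect. A pre/post test within one arm also responds to any change that both arms share, such as familiarity with the tests. As an illustration, suppose a shared shift of 0.2 SD of the change score, no treatment effect, and a paired t-test in 25 patients. The non-centrality is 0.2 × √25 = 1.0, and the test rejects 16% of the time, almost always in the favourable direction. For independent tests, the chance of at least one rejection is 1 − (1 − 0.161)^3 = 41% for three and 1 − (1 − 0.161)^4 = 50% for four. The 0.2 SD is assumed; with 0.1 SD the figures are 7.7% per test, 21% and 27%.

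**Step 4. Price of the alternatives.** For a between-arm t-test with 25 per arm and 80% power (non-central t), the detectable difference is 0.81 SD at alpha 0.05 and 0.98 SD at 0.05/4 = 0.0125. The normal approximation gives 0.79 and 0.95 SD. One named primary outcome therefore costs less sensitivity than dividing alpha over four.

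**The case against.** The strongest case on the other side has four parts.

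1. **This is a small proof-of-concept study, and aim b speaks of measuring an effect.** The label would justify calling efficacy exploratory, but the plan does not do so: Section 2 puts efficacy in the primary objective. The label lowers the severity and does not remove the point.

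2. **A reader might infer a false-efficacy risk of 11–19%.** The documents do not support that. The range counts significant results in both directions and depends on an assumed alpha and assumed correlations. The favourable-direction figure is about half. The upper end also needs four independent tests, which is implausible because the modified FFI (Attachment d) scores grip and TUG among its five components. At r = 0.9 the two-sided figure falls below 10%. This objection stands, and the size is stated accordingly.

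3. **A reader might infer that the plan lets any one positive result count as success.** No such rule is written. The accurate statement is that there is no rule at all, so a selective claim is neither planned nor prevented.

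4. **A reader might infer that naming a primary outcome alone brings the error back to 5%, or that STS is the only defensible choice.** Neither follows. With the paired tests of Section 6, a shared time effect can yield a false claim on a single outcome. As for STS, the background section reports that elastic-band training "has been shown to improve the patient's 30 second STS test and 8-foot TUG test", which supports TUG equally. Being listed first is not a scientific reason.

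**Conclusion.** The point holds, and should be dealt with before enrolment, although it does not prevent the trial from running. Efficacy is a stated part of the primary objective, the three lists name five measures between them, and no primary efficacy outcome, order or error control is given.

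At an assumed two-sided 0.05 per test and correlations of 0 to 0.7, the family-wise error is about 11–14% for three tests and 13–19% for four. The part that could be presented as benefit is about 5.5–7% and 6.5–10%, against 2.5% for a single test. These figures presume valid between-arm tests. Under the paired pre/post tests that Section 6 describes, any time or practice effect common to both arms would push the risk higher; the documents give no basis for saying by how much.

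**What to change.** - **Section 4d:** before enrolment, name one primary efficacy outcome. STS is a reasonable default: the background section cites it as improved by elastic bands, and its counting rule is the same in Attachment a and on the assessment form. TUG is equally supported by the background section, provided its scoring is first reconciled between Attachment c and the form.
- **Section 6:** test that outcome as the between-arm difference at the post-intervention assessment, and state the significance level. Both elements are needed; naming the outcome without changing the test leaves the shared-change problem in place.
- **Other measures, including modified FFI and LoPAQ activity:** list them as secondary in Sections 2, 4d and 6 alike. Report between-arm estimates with 95% confidence intervals and make no stand-alone efficacy claim from them. If tested claims on them are wanted, apply Holm's procedure.

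The cost is a few sentences, with no added patients, visits or measurements. The Section 6 change is one of substance, since it introduces a between-arm comparison that the plan does not now describe. The downside is that a lone positive secondary result could no longer be presented as proof of efficacy.

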- The Satellite Healthcare database will be used to identify all in-center hemodialysis patients at the Satellite Milpitas Dialysis Center
- This list of potential subjects will be approved by the Satellite Milpitas Medical Director who will screen to ensure they meet inclusion criteria.
- The study research associate (RA) and PI ([name]) will meet with the potential screened subjects in the dialysis center at the patient's weekly dialysis sessions
- The RA and PI will describe the study using a one-page information sheet and consent form as approved by the IRB.
- The RA and PI will offer the patient to take the information home and discuss with their relatives and significant others
- The RA and PI will then approach eligible participants again to consent to participate in the study. After consent is obtained, participants will be randomized into two groups using sequentially numbered opaque sealed envelopes.

e. Study Intervention

- 12 exercise physiologist consultations over 12 weeks
- Up to 3 exercise physiologists will implement an individualized resistance exercise program using elastic bands

f. Study Measures and Activities

- Subjects will meet with an exercise physiologist once weekly during one of their usual in-center HD sessions over a 3-month period.
- At the initial visit, the following physical function tests will be performed on the patient by EP: STS, HGST and TUG.
- At subsequent consultations, exercise physiologists will provide exercise plans and collect feedback on the exercises from the patients.
- EPs will tailor exercise routines to the individual patients based on a combined aerobic and resistance exercise program.

Aerobic Exercise

Participants will be asked to commence at a minimum of walking 3 times per week commencing at 20 minutes, and increasing both intensity and time up to 30 minutes x 3 times per week.

Resistance Exercise

Participants will be instructed to initially exercise various upper, core and lower body muscle groups using resistance bands for 1 set of 10 repetitions twice weekly. Intensity and repetitions of exercises will be adapted to participants' abilities throughout the 12 weeks. Warm up and warm down exercises will be included where relevant.

- Weekly progress notes and exercise checklists will be employed to monitor the types of exercises used. (see attachments f-h)
- The estimated duration for the appointments will be 30 minutes

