_____ minutes
10. In the past 7 days, how many hours were you in bed at night? _____ hours/night (average)

11. Do you work outside the home? no yes
if yes, does your job require you to do walking?
 no yes
if yes, your job require you to do physical exertion such as lifting?

(Johanson et al, Characterization of Physical Activity and sitting time among patients on Hemodialysis using a new physical activity instrument. Journal of Renal Nutrition 25:1, 2015 25-30)

f. EP Weekly Progress Note

How did the exercises go in the last week? At how many of your other sessions last week did you attempt to complete your exercises? How many of your aerobic exercises did you complete last week?

Have there been any noticeable changes that you have observed from our last meeting?

Is there anything that you are able to do now that you could not do before (endurance, strength, or flexibility)?

Have you experienced any symptoms or side effects from your exercise? If yes, what were they? (e.g., pain during any of the exercises? Any dizziness or light-headedness during or post-exercise?)

How can we modify the exercises from our last meeting?

Frequency	Intensity	Type	Time
-----------	-----------	------	------

What new exercises should we add or change for this upcoming week? (Document additional exercises for the new week and changes in prescription)

What are your exercise goals for the next week?

g. EP Exercise Plan

WARM UP						
ACTIVITY	SETS	REPS	TIME	DIST	INTENSITY**	NOTES

Aerobic Exercises		
Number of Attempts	Average Time	Average Distance

CORE BODY – STRENGTH TRAINING					
EXERCISES	SETS	REPS	WEIGHT/BANDS	REST TIME	NOTES

UPPER BODY – STRENGTH TRAINING					
EXERCISES	SETS	REPS	WEIGHT/BANDS	REST TIME	NOTES

LOWER BODY – STRENGTH TRAINING					
EXERCISES	SETS	REPS	WEIGHT/BANDS	REST TIME	NOTES

h. EP Weekly Checklist

INDEX VISIT CHECKLIST

1. Initial Intake visit

- Complete the PRE-Study Assessment form for both control and intervention patients.
- Provide intervention patient with an initial Exercise Plan form.
- Make a copy of the Exercise Plan form. Provide one to the patient and place one in the Patient Information binder.
- Scan the PRE-Assessment forms for all patients and email to [name] at [contact]

2. Weekly visit #1-11

- Complete the Progress Note form.
- If any alterations are made to the exercise plan, complete a new Exercise Plan form.

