- Make a copy of the updated Exercise Plan form. Provide one to the patient and place one in the Patient Information binder.

3. Weekly visit #12

- Complete the POST-Study Assessment form for both control and intervention patients.
- Complete the Progress Note form.
- Scan the POST-Study Assessment form for all patients and email to [name] at [contact]

4. Reminders

- Report any adverse events (side effects from exercise) to the Center Manager and email [name] at [contact]
- At any point, a patient may choose to leave the study. If this happens, notify the Center Manager [name] and email to [name] at [contact]

Pre and Post Intervention Assessment

Hand Grip Strength Measurements: Using the Handgrip strength dynamometer take the best of three measurements for the non-fistula arm. If both arms have fistulas, use the arm that is not currently being accessed. If no fistula is present, use the non-dominant arm. Chart whether the left or right arm is used for the test. For the post-assessment make sure it is the same hand used in the pre-assessment. Pause 10-20 seconds between each test.

Handgrip Strength		
Test 1:	Test 2:	Test 3:
Average:		Hand Used:

Timed Up and GO (TUG): Record time in seconds for the patient to walk 8 feet in a straight line and return to a seated position. Patient is allowed one practice run. Two are counted. Note the average of the two. Chart if an assistance device such as a walker or cane is needed and note the type of assistance device.

Timed Up and Go (TUG) (seconds)	
Trial #1:	Trial #2:
Average:	Assistance Device:

Sit-to-Stand: Have the patient sit with arms crossed over the chest stand up and sit down as quickly as possible. Record the number of times they can go from sitting to standing in 30 seconds.

Sit-to-Stand (Repetitions/ Time)	
# of repetitions:	Repetitions/Time:

Low Physical Activity Questionnaire: Administer the questionnaire on the following page as instructed. Scan and email back results of this and the above physical function tests to [contact]. [see attachment e]

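### The efficacy analysis specifies only within-patient pre/post tests and no comparison between the randomised arms, so it does not estimate the effect that aim b asks for

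*Combined protocol and SAP*

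**What the plan says.** Section 4 describes a proof-of-concept randomised controlled trial, and Section 4c sets the size at "n=50 (25 intervention - 25 control". Under Section 5d, "participants will be randomized into two groups using sequentially numbered opaque sealed envelopes". The primary objective in Section 2 covers both feasibility and efficacy. Aim b is to "Measure the effect of an exercise physiologist collaboration and intradialytic exercise on the physical function of HD patients", by sit-to-stand (STS), handgrip, timed up and go (TUG) and "patient physical activity based off of the Low Physical Activity Questionnaire".

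The efficacy outcome in Section 4d is change in STS, handgrip and TUG, with no mention of a contrast between arms.

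Section 6 contains the only inferential method: "Paired t-test or Wilcoxon-sign-rank will be used to compare the pre and post intervention STS, Hand Grip Test, TUG", extended in the same sentence to the modified Fried Frailty Index (FFI), with the choice of test left to the distribution of the data. It then adds: "Patients who drop out or withdraw from the study will be included in the final outcomes with intention-to-treat analysis".

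The checklist in attachment h covers both arms at both times: "Complete the PRE-Study Assessment form for both control and intervention patients" at intake and "Complete the POST-Study Assessment form for both control and intervention patients" at visit 12.

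**The concern.** A paired t-test or Wilcoxon signed-rank test asks whether patients changed. Aim b asks whether the programme changed them, and in a randomised trial that question is answered by the difference between arms. Section 6 does not say whether the paired test is run in the intervention arm, in each arm or in all 50 patients pooled. None of these estimates the between-arm effect.

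If both arms improve for a reason unrelated to the programme, such as familiarity with the tests or a time trend, the planned test can report efficacy where there is none. Running it in each arm and contrasting the two p-values does not repair this, because significant in one arm and not in the other is not a test of the difference.

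The feasibility outcomes are unaffected. Adherence and exercise-related adverse events can properly be described within the intervention arm.

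**Working it through.** **Step 1: which comparisons are specified.**

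| Element | Where | Compares arms? |
|---|---|---|
| Randomisation, 25 v 25 | 4c, 5d | Sets up a comparison |
| Efficacy outcome: change in STS, handgrip, TUG | 4d | No contrast defined |
| Paired t or signed-rank test, pre v post | 6 | No, within patient |
| Intention-to-treat sentence | 6 | No, it says who is included |
| Pre and post forms in both arms | Attachment h | Data allow a comparison |

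No two-sample test, ANCOVA, mixed model or difference in change appears in the documents. The data can support a between-arm estimate, and the stated analysis does not make one.

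**Step 2: how often the paired test misleads (illustration).** From the documents: n = 25 per arm, 50 in total. Assumed, because the documents give no value: two-sided 5% level, equal SDs before and after, every patient completing, true treatment effect zero, pre/post correlation r, and a gain g (in SDs of the measurement) shared by both arms.

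- SD of change = √(2(1 − r)): 1.000 at r = 0.5, 0.894 at 0.6, 0.775 at 0.7, 0.632 at 0.8.
- Noncentrality of the paired t-test = g√n / √(2(1 − r)), on n − 1 degrees of freedom.
- Example: g = 0.2, n = 25, r = 0.7 gives 0.2 × 5 / 0.775 = 1.29, and P(|t| > 2.064) on 24 df is 23.6%.

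Probability of a significant paired test with no treatment effect:

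| Shared gain | n = 25, r = 0.5 / 0.6 / 0.7 / 0.8 | n = 50 pooled, same r |
|---|---|---|
| 0.1 SD | 7.7 / 8.4 / 9.5 / 11.8% | 10.7 / 12.1 / 14.6 / 19.5% |
| 0.2 SD | 16.1 / 18.9 / 23.6 / 33.0% | 28.4 / 34.1 / 43.3 / 59.2% |
| 0.3 SD | 30.2 / 36.3 / 46.0 / 62.4% | 54.8 / 64.2 / 76.6 / 90.8% |

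At zero shared gain the rate is 5%. The signed-rank test behaves similarly: by simulation in the intervention arm at r = 0.7 (4,000 trials per cell), 8.5%, 22.5% and 44.7% for the three gains. Over 20,000 simulated trials per cell, with r of 0.5, 0.7 and 0.8 and gains from 0 to 0.3 SD, ANCOVA rejected in 4.8–5.2% and a between-arm t-test of change in 4.8–5.1%.

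**Step 3: paired tests run arm by arm.** Take a shared change of 0.4 SD of change and no treatment effect. Each arm is significant with probability 0.484, so significant improvement in the intervention arm together with non-significance in control has probability 0.484 × (1 − 0.484) = 0.25.

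**Step 4: precision of the alternatives, at assumed r = 0.7.** 95% CI half-widths in SDs:

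- Within-arm change: 2.064 × 0.775 / √25 = 0.32.
- Between-arm difference in change: 2.011 × 0.775 × √(2/25) = 0.44.
- Between-arm ANCOVA: 2.012 × √(1 − 0.7²) × √(2/25) = 0.41.

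The within-arm interval is narrower, but it describes a different quantity and is not a more precise estimate of the treatment effect. The difference detectable with 80% power at 25 per arm, for r from 0.5 to 0.8, is 0.70 to 0.49 SD by ANCOVA and 0.81 to 0.51 SD by comparison of change.

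**The case against.** The best reply is that a trial described as randomised and controlled, with 25 controls assessed before and after and an intention-to-treat statement, implies a comparison of arms. The intention may well have been there. But no estimator or test for it is named, and the tests that are named do something else. The claim is therefore about what is specified, and to that extent it stands.

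A second reply is that this is a small proof-of-concept study with feasibility listed first. That justifies modest power and an emphasis on confidence intervals. It does not justify an efficacy analysis without the control arm when efficacy is part of the primary objective.

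Third, the illustrative rates rest wholly on assumed inputs, and TUG already has a practice trial, which may reduce a learning effect. Both points are fair. The STS and handgrip instructions describe no practice trial, but nothing in the documents supports a particular shared gain. The pooled reading, which gives the largest rates, is also the least natural for a controlled design. The rates show a mechanism and do not predict what this trial would find.

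**Conclusion.** The concern holds and should be corrected before analysis. Section 6 states a method that does not answer aim b, which goes beyond missing detail. This conclusion rests on the text alone.

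Its possible size depends on the assumptions in the working. With no treatment effect, a shared gain of 0.1 to 0.3 SD and correlations of 0.5 to 0.8, the paired test in the intervention arm is significant in about 8% to 62% of trials, against about 5% for a between-arm test. If both arms truly have no change, the paired test keeps its 5% level, but it still gives no between-arm estimate.

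A smaller gap of the same kind concerns the Low Physical Activity Questionnaire (LoPAQ). Aim b names it, Section 4d does not list it as an efficacy outcome, and Section 6 analyses it only through its contribution to the modified FFI.

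**What to change.** Replace the paired-test sentence in Section 6 with wording such as: *For STS, handgrip and TUG, the treatment effect is the between-arm difference in the post-intervention value with 95% CI, from ANCOVA on randomised arm and the baseline value of the same test, with patients analysed in the arm assigned. A permutation or rank-based test of the same contrast is a sensitivity analysis.* A between-arm comparison of change is also valid; ANCOVA is preferred for precision. Report within-arm pre/post change as description only.

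Points to settle at the same time:

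- **Scoring.** Fix one score per test. TUG is the faster of two trials in attachment c and their average in attachment i. Handgrip is an average in attachment b, while attachment i asks for the best of three and also has a box for the average.
- **LoPAQ.** Either name one activity summary and compare it between arms with baseline adjustment, or reconcile aim b with Section 4d. Attachment e gives items without a summary score; attachment d gives only a yes/no low-activity rule.
- **Modified FFI.** Compare arms only if its items are collected in both arms at both times. Section 5f places it in both groups at the start; the schedule shows a second assessment without naming arms. The weight-loss and energy items are in attachment d and not on the pre/post form.
- **Missing post values.** State the method; the intention-to-treat sentence gives none.
- **Timing.** Confirm the week of the post assessment. The schedule as extracted appears to show week 11 and the checklist says visit 12, which may be an artefact of the table.

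The cost is a wording change and a little more analysis. STS, handgrip, TUG and LoPAQ need no new data. The reported interval will be wider (about 0.41 v 0.32 SD at an assumed correlation of 0.7), but it will be an interval for the treatment effect.
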